5.6.1. Prohibited and/ or Restricted Medications

Use of any medication, herbal supplements or other over-the-counter product known to: have an immunomodulatory effect (e.g. astragalus); or known to affect pigmentation including topical products on the face that could potentially lighten the skin (e.g., hydroquinones, azaleic acid, Kojic acid, mequinol, retinoids, niacinamide, arbutin) or known to temporarily dye the skin on the face and treated areas of the neck (such as dihydroxyacetone or hennas) are prohibited throughout the study. Subjects treated with depigmenting agents such as monobenzyl ether or hydroquinone are excluded from the study.

The following medications and therapies require a specific washout period prior to study entry and **are not permitted during the study:**

1. Use of any biologic, investigational therapy or procedure for vitiligo within 12 weeks or 5 half-lives (whichever is longer) of screening (Visit 1).
2. Use of laser or light-based vitiligo treatments, including tanning beds, within 8 weeks of screening (Visit 1). Subjects with regular outdoor light exposure not for the intent of tanning may participate. NB-UVB treatments may be administered according to the Standard of Care protocol for the treatment of vitiligo after the subject has completed Visit 9. NB-UVB treatments should be recorded in the source documents and on the Concomitant Therapies Log of the eCRF.
3. Use of immunomodulating oral or systemic medications (e.g., corticosteroids, methotrexate, cyclosporine) or topical treatments that may affect vitiligo (e.g., corticosteroids, tacrolimus/ pimecrolimus, retinoids) within 4 weeks of screening (Visit 1).
4. Use of any prior concomitant therapy not listed above that may interfere with the objective of the study as per the discretion of the investigator, including drugs that cause photosensitivity or skin pigmentation (e.g., antibiotics such as tetracyclines, sulfas, tranexamic acid) within 8 weeks of screening (Visit 1).
5. Subjects who have previously received oral or topical JAK inhibitors.

5.7. Subject Identifier (SI)

The Investigator will assign a unique five-digit subject identifier (SI) to each subject at Screening (Visit 1).

The SI format will be NN-NNN, using leading zeros as appropriate, where:

- The first 2 digits are the investigational center site number assigned by Aclaris.
- The final 3 digits are the subject number (SN), assigned in ascending numerical order by the Investigator or designee, without omitting or repeating any number, starting with 001. For example, the SI for the twenty-third subject that signs an informed consent form at site number 01 would be 01-023. The subject will be identified using the SI in all study documentation for the duration of the study.

5.8. Replacement Subjects

Subjects who are receive study medication at Visit 2 and do not complete the study will not be replaced.

5.9. Subject Withdrawal Criteria

Subjects will be informed that they are free to withdraw from the study at any time and for any reason. The investigator may remove a subject from the study if, in the investigator's opinion, it is not in the best interest of the subject to continue the study. Examples of other reasons subjects may be discontinued from the study are: a change in compliance with an inclusion or exclusion criterion, occurrence of AEs, occurrence of pregnancy, use of a prohibited therapy or subject is unwilling or refuses to continue with the protocol defined study visits and/or subject withdraws consent (Refer to Section 9.2.4 for study medication discontinuation criteria).

In case of premature discontinuation of study participation, all efforts will be made to perform all Visit 10 (Week 24) assessments or if continuing for the additional 24 weeks, Visit 15 (Week 52). The date the subject is withdrawn from the study and the reason for discontinuation must be recorded in the subject's electronic case report forms (eCRFs). All withdrawn subjects with ongoing AEs will be followed until the event has resolved or stabilized, until the subject is referred to the care of a local health care professional, or until a determination of a cause unrelated to the study medication or study procedures is made.

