8.2.1. ECGs

Standard 12-lead ECGs will be performed by a qualified staff member at Screening (Visit 1), Baseline (Visit 2), Day 8 (Visit 3), Visits 5-10, Visit 11 (if applicable) and if continuing for the additional visits, Visit 15. The ECGs must be obtained using a standard 12-lead ECG with a 10mm/mV amplitude, at 25mm/sec and a 5-10-second duration. To ensure a steady heart rate the subject must rest quietly in the supine position for at least 5 minutes prior to performing the ECG.

A central lab, eResearchTechnology, Inc. (ERT), will provide ECG equipment, supplies and site training. In addition, ERT will process ECGs received by the sites and report results via a secure study portal. The ECG results will be interpreted by a qualified health professional (evaluator) and the interpretation reported either directly on the tracing or in a separate report. The evaluator will interpret the results of every ECG and define the ECG as “normal” or “abnormal”. Variations such as minor ST changes (*i.e.*, <0.5mm depression) and early re-polarization are considered normal.

The investigator must review the evaluator’s interpretation of each subject’s screening ECG prior to Baseline (Visit 2). The investigator will review, sign and date the evaluator’s interpretation of all ECG reports in a timely manner and comment on the clinical significance of any result that is defined by the evaluator as abnormal.

Any abnormalities that are, in the opinion of the investigator, clinically significant, must be reported as history if found prior to the start of the first study medication application or as an AE if found after the start of the first study medication application (see Section 9.1.1).

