9.1.4. Adverse event reporting period

The investigator must start reporting non-serious AEs with the subject's first study medication application and continue reporting until the end of the subject's last study visit. Reporting for SAEs must start when the subject signs the ICF and continue until the end of the subject's last visit.

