9.2.3. Safety Monitoring Discontinuation Criteria

Any subject who develops any of the following ECG findings during the active treatment phase will be instructed to stop study medication and will be withdrawn from the study:

- A post-study medication ECG result where the evaluator’s interpretation shows any of the following:

- Clinically significant rhythm disturbance other than sinus rhythm or ectopic supraventricular rhythm (ectopic atrial rhythm)
- Clinically significant conduction disturbance including PR >240msec, pre-excitation (delta wave and PR <120msec), second degree or higher AV block
- New finding of QRS>120ms (if not present at screen. For example, subjects with Right Bundle Branch Block at screening would not need to be withdrawn from the study if their subsequent ECGs remained unchanged).
- Evidence of QT-interval prolongation, defined as an increase in the QTcF interval>60ms from Visit 1
- Acute signs of ischemia or infarction
- Any ECG abnormality which may, in the opinion of the investigator, represent a new medical issue of concern

Site staff must perform protocol-required procedures for trial discontinuation and follow-up.

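### Subjects who leave the study before Week 24 have no planned safety contact after their exit visit, and AE and SAE reporting closes at that visit

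*Combined protocol and SAP*

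**What the plan says.** **Early leavers.** Section 5.9 states that on early departure "efforts will be made to perform all Visit 10 (Week 24) assessments or if continuing for the additional 24 weeks, Visit 15 (Week 52". The Visit 10 set applies before the extension and the Visit 15 set within it. Neither is timed from the last application, and no contact after the set is named. Under Section 6.4.4 the Visit 10 set includes an AE query, vital signs, ECG, laboratory tests, a urine pregnancy test and local tolerability.

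**After exit.** Section 5.9 adds: "All withdrawn subjects with ongoing AEs will be followed until the event has resolved or stabilized". This covers events already present at withdrawal.

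**Reporting period.** Section 9.1.4 says: "Reporting for SAEs must start when the subject signs the ICF and continue until the end of the" subject's last visit. Non-serious AE reporting ends at the same point. Section 9.2.2 ties the investigator's SAE duty to events within that period.

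**Completers.** Those who finish Week 24 and decline the extension attend Visit 11 (Section 6.4.5). Those who finish Week 48 attend Visit 15 (Section 6.4.9). Both visits include an AE query.

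**ECG withdrawals.** Section 9.2.3 removes a subject from the study on two purely numeric findings: "Evidence of QT-interval prolongation, defined as an increase in the QTcF interval>60ms from Visit 1" and "New finding of QRS>120ms (if not present at screen" [parenthesis continues]. It then says: "Site staff must perform protocol-required procedures for trial discontinuation and follow-up". Section 8.2.1 makes clinical significance the test for recording an ECG finding: "Any abnormalities that are, in the opinion of the investigator, clinically significant, must be reported as history" if they predate treatment, "or as an AE if found after the start of the first study medication application".

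**The concern.** Safety is part of the primary objective (Section 4.1), and Section 6.1 plans 4 weeks of follow-up after treatment. That period is built into the visit schedule for completers but not for subjects who leave before Week 24. Extension leavers are assigned the post-treatment set, whereas pre-Week-24 leavers are assigned the end-of-treatment set, and no reason is given for the difference.

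Some early leavers will have gone for a safety reason, and treated subjects who do not complete are not replaced (Section 5.8). In an uncontrolled study of 33 subjects, a new event in the weeks after stopping would be looked for in completers and not in these subjects. The AE tables would then rest on unequal observation, without showing it.

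**Working it through.** **1. The plan's own figure.** Sections 6.1 and 6.3 give 4 weeks of post-treatment follow-up and the nominal visit days.

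- Visit 11 minus Visit 10: 197 − 169 = 28 days.
- Visit 15 minus Visit 14: 365 − 337 = 28 days.

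Both equal 4 weeks, so the stated figure is reproduced. These intervals run from the last treatment visit, which is taken here as the end of dosing.

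**2. Range within windows.**

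- Visit 10 is Day 169 ± 4 (165-173) and Visit 11 is Day 197 ± 14 (183-211). Shortest: 183 − 173 = 10 days. Longest: 211 − 165 = 46 days.
- Visit 14 is Day 337 ± 7 (330-344) and Visit 15 is Day 365 ± 7 (358-372). Shortest: 358 − 344 = 14 days. Longest: 372 − 330 = 42 days.

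**3. Leavers before Week 24.** The off-drug time covered is the day of the exit set minus the day of the last application. Section 5.9 fixes neither, so no minimum is guaranteed. It is 0 days if the set is done on the last dosing day. After the set, no further reporting time is planned.

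**4. Could Visit 11 fill the gap?** Section 6.4.4 schedules Visit 11 for subjects who do not consent to the extension, but Section 5.9 assigns an early leaver only the Visit 10 assessments. Visit 11 is also counted from Visit 2. For a subject who leaves at Week 8 it would fall 28 − 8 = 20 weeks later, not 4.

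**5. What other sections cover after exit.**

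| Situation | Covered by |
|---|---|
| AE ongoing at withdrawal | 5.9 |
| Related AE unresolved at last visit | 9.2.1 |
| SAE that began in the reporting period | 9.2.2 |
| Table 1 laboratory abnormality | 9.2.4.1 |
| Clinically significant ECG finding | AE under 8.2.1, then 5.9 |
| Pregnancy with exposure | 10.2, if it becomes known |
| New AE after exit | Nothing |
| New SAE after exit | Only the SAE undertaking in the investigator's statement at the front of the protocol |
| Withdrawal on the QTcF or QRS number, judged not clinically significant | The exit-set ECG, at no fixed time |

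Sections 9.2.3 and 10.2 mention follow-up procedures after discontinuation, but no section defines a post-withdrawal visit.

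**6. Where ECG withdrawals would fall.** Scheduled on-treatment ECGs after baseline are at Visits 3, 5, 6, 7, 8, 9 and 10, which makes 7. Six of them precede Visit 10, and none is scheduled at Visits 12-14. Withdrawals prompted by a scheduled ECG would therefore fall mainly in the pre-Week-24 group.

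**7. Size of the group.** Section 11.1 gives no dropout rate. Assuming that 5% to 20% leave before Week 24: 0.05 × 33 = 1.65 and 0.20 × 33 = 6.6, or about 2 to 7 subjects. No rate of new events after exit is given, so the number missed cannot be estimated.

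**The case against.** The strongest reply is that little is lost. The exit set already contains an AE query, laboratory tests and an ECG, and known problems are followed afterwards. Completers are not guaranteed 28 days either, and nothing in the documents shows that risk lasts 28 days after a topical facial application. The study is a descriptive pilot with no planned comparison of leavers and completers. This stands as a limit on severity. It does not explain why the plan's own 4-week follow-up is omitted for one group.

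Four stronger readings are tempting, and the documents do not support them.

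- **Everyone who does not enter the extension lacks follow-up.** Those who finish Week 24 and decline the extension are scheduled for Visit 11.
- **Everyone taken off drug for safety is lost.** Section 9.2.4.2 stops study medication without ordering withdrawal from the study, so such subjects could remain through Visit 11, although the cross-reference in 5.9 leaves some ambiguity. Laboratory abnormalities are also followed under 9.2.4.1, so laboratory withdrawals are not a separate gap.
- **Leavers have a pregnancy-testing gap that completers do not.** Completers are tested nominally at day 28, and as early as day 10 or 14, also before the 30-day contraception period ends.
- **SAEs after exit cannot reach the sponsor.** The investigator's statement promises notification of any SAE with no end date. It is a passive backstop: nobody is asked to look, and 9.2.2 is narrower.

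The ECG case is also thin. It needs a mandated withdrawal that the investigator nevertheless judges not clinically significant, and an exit ECG is still planned. What remains is that this ECG need not be taken after drug is stopped.

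**Conclusion.** The point holds for subjects who leave the study before Week 24. Their exit set has no timing from the last dose and no contact follows it. Events that begin after the set are not actively sought and fall outside the protocol's reporting period. Completers are asked about new events nominally 28 days after treatment ends.

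The severity is minor, and the change is a cheap improvement. The group would be about 2-7 of 33 subjects only under the assumed 5-20% dropout, and the loss of 0 covered off-drug days is a worst case that depends on when the exit set is done. It would be wrong to infer that the safety results are known to be biased, because the documents give no rate of new events after exit.

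Extension leavers are outside the main point. For them, the only omission noted is that 5.9 does not say when the Visit 15 set is done relative to the last dose.

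**What to change.** - **Section 5.9.** For early leavers who have not withdrawn consent, add one telephone contact about 28 days after the last application to ask about new AEs and SAEs, unless the exit set is itself done at about that time. State when the exit set, Visit 10 or Visit 15, is done relative to the last application.
- **Section 9.1.4.** Run AE and SAE reporting to the later of the last visit or that contact.
- **Section 9.2.3.** Say that the required follow-up includes this contact. For subjects withdrawn on the QTcF or QRS number, say that the exit-set ECG already planned is taken after drug is stopped.

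No extra pregnancy test or repeat laboratory test is needed for this point.

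The cost is wording in three sections and one call per early leaver, about 2-7 calls at the assumed 5-20%. Some subjects will decline, and a call does not detect silent ECG or laboratory changes.

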5.10. Study Termination

This study may be terminated prematurely in whole or in part due to a change in the benefit/risk profile for ATI-50002 Topical Solution such that continuation of the study would not be justified on medical or ethical grounds. This determination may be made by the Study Investigators in conjunction with the Sponsor, or by IRB or the U.S. Food and Drug Administration (FDA). The Sponsor may also elect to terminate the study if enrollment is sufficiently slow to prevent the completion of the study in an acceptable timeframe, or if ATI-50002 development is discontinued.

If the study is terminated prematurely, the Sponsor will notify the Study Investigators and the FDA. The Investigator must promptly notify all enrolled subjects and the IRB of study termination.

6. INVESTIGATIONAL PLAN

6.1. Overall Study Design

This Phase 2, multicenter, open label study is designed to evaluate the safety, tolerability and efficacy of ATI-50002 Topical Solution in subjects with facial non-segmental vitiligo. Subjects will be required to have a clinical diagnosis of new onset or actively progressing non-segmental facial vitiligo involving at least 0.25% TBSA (excluding upper and lower eyelids, mucosal lip areas, beard [if applicable]; and forehead and chin areas covered by the stereotactic positioning device for photography) with at least one area of the face with normal pigmentation. The face is defined as the area from the border of the hairline, not including hair bearing skin to the jawline. Thirty-three subjects will receive ATI-50002 Topical Solution, 0.46%, BID for up to 48 weeks.

During the screening period, subjects will be assessed for eligibility to receive study medication. Eligible subjects will apply study medication to the vitiliginous areas of the face and neck including $\frac{1}{2}$ " margin around these areas (excluding the upper and lower eyelids and mucosal areas of the lips) twice-a-day for up to 48 weeks. Assessment of response to treatment will be performed using the Canfield 2-D Photographic image analysis, Facial VASI, Vitiligo Noticeability Scale, VitiQoL, and Subject Vitiligo Satisfaction Scale. These assessments will occur as specified in the Schedule of Assessments. Subjects will be seen at up to 15 study visits, including up to 48 weeks of active treatment followed by 4 weeks of post treatment follow-up.

Safety and tolerability will be evaluated throughout the study by assessment of electrocardiograms (ECG), clinical laboratory tests, adverse events including local site reactions and vital signs.

6.2. STUDY PROCEDURES

The investigator, a designated and appropriately trained staff member, independent evaluator(s), or the subject, will perform the study assessments according to the schedule of assessments (Section 6.3). The same staff member should perform the assessments for a given subject throughout the study. If this becomes impossible, an appropriate designee with overlapping experience with the subject and study should perform the assessments. The same lighting conditions and subject positioning should be used for all evaluations for a given subject.

6.3. Schedule of Assessments

	Screening	Baseline	Treatment									Post-Treatment
	Visit 1	Visit 2	Visit 3	Visit 4	Visit 5	Visit 6	Visit 7	Visit 8	Visit 9	Visit 10	Visit 11	
Week		0	1	2	4	8	12	16	20	24		28
Treatment Day	-28 to 0	1	8	15	29	57	85	113	141	169		197
Treatment Window(days)	N/A	N/A	± 4	± 4	± 4	± 4	± 4	± 4	± 4	± 4		± 14
Informed consent ¹	X											
Inclusion/exclusion criteria	X	X										
Physical exam ²	X											X
Demographics & medical history	X											
Vitiligo History	X											
Vital signs ³	X	X	X	X	X	X	X	X	X	X		X
Clinical CBC, Chemistry, Virology, Serum Pregnancy, Urinalysis ⁴	X ⁴	X	X		X	X	X	X	X	X		X
Urine pregnancy test ⁵		X			X	X	X	X	X	X		X
ECG	X	X	X		X	X	X	X	X	X		X
Facial BSA	X	X										
Facial Vitiligo AreaScoring Index (F-VASI) ⁶		X Pre-dose			X	X	X	X	X	X		X
Total body VASI	X	X Pre-dose						X				X
Canfield 2D Photography ⁷		X			X	X	X	X	X	X		X
Vitiligo Noticeability Scale (VNS)					X	X	X	X	X	X		X
Subject Vitiligo Satisfaction Scale ⁸ (SVSS)							X	X	X	X		X
VitiQoL		X					X	X	X	X		X
Local Tolerability Assessment (LTA) Investigator		X Pre and post dose	X	X	X	X	X	X	X	X		X
Local Tolerability Assessment (LTA) Subject		X Pre and post dose	X	X	X	X	X	X	X	X		X
Subject Eligibility Confirmation		X										
Subject instructions ⁹		X	X	X	X	X	X	X	X			
Dispense study medication ¹⁰		X	X	X	X	X	X	X	X			
Collect, medication, assess compliance ¹⁰			X	X	X	X	X	X	X	X		
In office study medication application ¹¹		X										
Concomitant therapies	X	X	X	X	X	X	X	X	X	X		X
Adverse events		X	X	X	X	X	X	X	X	X		X

	Screening	Baseline	Treatment								Post-Treatment
	Visit 1	Visit 2	Visit 3	Visit 4	Visit 5	Visit 6	Visit 7	Visit 8	Visit 9	Visit 10	Visit 11
Week		0	1	2	4	8	12	16	20	24	28
Treatment Day	-28 to 0	1	8	15	29	57	85	113	141	169	197
Treatment Window(days)	N/A	N/A	± 4	± 4	± 4	± 4	± 4	± 4	± 4	± 4	± 14
For Subjects Continuing to Visit 12-15:											
Revised ICF for Visits ¹²⁻¹⁵										X ¹²	X ^{12, 14}
Subject instructions ⁹										X	X ¹⁴
Dispense study medication ¹⁰										X ¹³	X ^{13,14}
¹ A written, signed ICF must be obtained from each subject prior to performing any study related procedure (i.e., prior to performing vital signs, standardized photography, clinical laboratory sampling or urine pregnancy tests).											
² A physical exam includes: general appearance, examination of head, eyes, ears, nose and throat, respiratory, cardiovascular, abdominal, neurological, musculoskeletal, lymphatic and skin assessment.											
³ Vitals signs include: oral or ear temperature, blood pressure, heart rate, respiration rate (height and weight at screening only).											
⁴ Clinical laboratory sampling include: CBC, Chemistry with lipids, and Urinalysis. Quantiferon Gold, HIV, Hepatitis B and C, TSH, T3, Free T4 and Serum Pregnancy should be done at screening visit only. Subjects with any Screening laboratory values meeting the Study Medication Interruption Criteria found in Table 1 must have repeat lab testing performed with results meeting the minimum criteria for resumption in order to initiate treatment at Baseline (Visit 2).											
⁵ UPT must be performed in WOCBP prior application of study medication at Baseline (Visit 2) and must be negative for the subject to continue in the study. UPTs in WOCBP must also be obtained at Visit 5, 6, 7, 8, 9, 10, and 11. WOCBP must have a negative serum pregnancy test at Screening (Visit 1) and a negative UPT at baseline (Visit 2) prior to application of study medication.											
⁶ F-VASI must be determined at Baseline (Visit 2) and Visits 5-11. During the baseline visit, F-VASI should be determined prior to application of study medication.											
⁷ Canfield photography will be performed at Prior to dosing at Baseline (Visit 2) and at Visits 5, 6, 7, 8, 9, 10 and 11.											
⁸ Subjects will complete the Subject Vitiligo Satisfaction Scale at Visits, 7, 8, 9, and 10 and at post-treatment Visit 11.											
⁹ The study staff must instruct the subject to apply study medication according to the instructions in APPENDIX 1.											
¹⁰ The study staff must weigh the study medication bottle(s) with cap prior to dispensing to the subject and after the study medication bottles are returned to the investigational site. Staff should review the usage based on the weight of the bottle and counsel the subject as necessary.											
¹¹ At Baseline (Visit 2), the first application of study medication should be performed by the subject under the supervision of the study staff and the subject should be observed for 20 minutes after the initial application.											
¹² A written, signed ICF with the additional visits (Visits 12 -15) must be obtained from each subject prior to performing any Visit 12 study related procedure.											
¹³ For subjects who consent to continue for additional study visits, Visit 12-15, study medication should be dispensed.											
¹⁴ If a subject completes Visit 10 prior to implementation of Amendment 3, they may return for Visit 11 to sign consent, receive additional study medication and have the other tests performed as detailed in the Schedule of Assessments.											

Procedures	Open-Label Treatment			Post-Treatment
	Visit 12	Visit 13	Visit 14	Visit 15
Week	32	40	48	52
Treatment Day	225	281	337	365
Treatment Window(days)	± 7	± 7	± 7	± 7
Physical exam ²				X
Vital signs ³	X	X	X	X
Clinical CBC, Chemistry, Urinalysis ⁴	X	X	X	X
Urine pregnancy test ⁵	X	X	X	X
ECG				X
Facial Vitiligo Area Scoring Index (F-VASI) ⁶	X	X	X	X
Total body VASI			X	
Canfield 2D Photography ⁷	X	X	X	X
Vitiligo Noticeability Scale (VNS)	X	X	X	X
Subject Vitiligo Satisfaction Scale ⁸ (SVSS)	X	X	X	
VitiQoL			X	
Subject instructions ⁹	X	X	X	
Dispense study medication ¹⁰	X	X		
Collect, medication, assess compliance ¹⁰	X	X	X	
Concomitant therapies	X	X	X	X
Adverse events	X	X	X	X

